**I. Background and rationale**

250,000 ventral hernia repairs are performed in the United States every year, and hernia recurrence, as well as surgical site occurrences (SSOs), remain a significant problem. When hernias recur and require reoperation, the subsequent risk of recurrence increases significantly. In fact, Luijendijk *et al* have shown that the 5-year risk of hernia recurrence increases stepwise with every reoperation (24% after the first reoperation, 35% after the second reoperation, 39% after the third reoperation), and this underscores the importance of performing the best possible hernia repair the first time. In order to design the operation with the best possible odds of success, high-quality level I evidence is needed. There is a scarcity of high-quality, randomized-controlled trials in the field of ventral hernia repair.

One aspect of hernia repair that still contains significant uncertainty due to the scarcity of high-quality data is the ideal type of mesh. Meshes used in hernia repair fall into two broad categories: synthetic and biologic. Synthetic meshes add strength to the fascial repair, but are plagued by a high rate of infection and formation of enterocutaneous fistulas. This led to the development of biologic meshes. These usually consist of human or animal dermis that has been treated to remove cells, thus leaving a collagen matrix and making the material non-immunogenic. They are less prone to fibrous encapsulation than synthetic meshes. In addition, those biologic meshes serve as scaffolds that allow ingrowth of new tissue, including new blood vessels. This makes them less prone to infection than synthetic meshes. The Ventral Hernia Working Group (VHWG) recommends using a biologic mesh rather than a synthetic mesh in patients with a VHWG hernia grade of 2 or above. Although many biologic meshes exist, it is unclear which one provides optimal ventral hernia repair with the lowest rate of SSOs.

Some biologic meshes commonly used in abdominal wall reconstruction include:

-Strattice: non-cross-linked porcine acellular dermal matrix (LifeCell Corp., Branchburg, NJ)

-XenMatrix: non-cross-linked porcine acellular dermal matrix (Davol, Warwick, RI)

-SurgiMend: non-cross-linked bovine acellular dermal matrix (TEI Bioscience, Inc., Boston, MA)

- FlexHD: human acellular dermal matrix (Ethicon, Somerville, NJ)
- AlloDerm: human acellular derman matrix (LifeCell Corp., Branchburg, NJ)
- AlloMax: human acellular derman matrix (Davol, Warwick, RI)
- Permacol: cross-linked porcine acellular dermal matrix (Covidien, Mansfield, MA)

It is known that the lowest recurrence and complication rates are achieved when the fascia is closed primarily in the midline, with additional reinforcement using mesh. Closure of the native fascia can be achieved via primary advancement and suture in the case of small hernias, or component separation (as described in Ramirez *et al*) in the case of larger hernias. Meshes can be placed as an overlay (superficial to the fascial closure), underlay (deep to the fascial closure), or bridge (in cases where the fascia cannot be primarily closed)

The senior author ([name]) performs hernia repair using a technique similar to the Minimally-Invasive Component Separation with Inlay Bioprosthetic Mesh technique (MICSIB) described by Butler *et al*. The technique involves division of the external oblique aponeurosis just lateral to the semilunar line via a narrow subcutaneous tunnel, without significant subcutaneous undermining. This can be performed unilaterally or bilaterally. This is followed by placement of biologic mesh for reinforcement, in an intraperitoneal or retro-rectus plane, with wide overlap with the native fascia (this is a departure from the MICSIB technique, where the mesh is placed in the pre-peritoneal plane). Finally, the rectus muscles are advanced medially and the fascia is primarily closed over the mesh. This technique improves skin flap vascularity by preserving the myocutaneous perforators to the abdominal skin, and by minimizing subcutaneous dissection and dead space, which can result in fluid collections. In their evaluation of 38 patients with large abdominal hernias, Butler *et al* applied the MICSIB technique, achieving primary musculofascial closure with inlay mesh in 31 patients and bridged repair with mesh in 7 patients. Mean follow-up was 12.4 months. There were no hernia recurrences. There was one bulge. There were no seromas, and there were two instances of skin necrosis (compared to a rate of 20% in the literature for standard component separation). In a subsequent report comparing minimally-invasive component separation to standard open component separation, Butler *et al* found the minimally-invasive technique to result in far fewer instances of skin dehiscence and wound healing complications. The same group has also found that primary repair of the fascia with mesh reinforcement results in far fewer instances of hernia recurrence than cases where the fascia cannot be primarily closed and where mesh is used as a bridge.

In the MICSIB study by Butler *et al*, all patients received non-cross-linked acellular porcine dermal matrix bioprosthetic mesh. There are several retrospective studies comparing various types of allogenic and xenogenic bioprosthetic meshes in abdominal wall reconstruction. Non-cross-linked porcine mesh has been shown to be superior to human acellular dermis, resulting in fewer instances of laxity/bulge. Non-cross-linked porcine acellular dermis has also been shown to be superior to cross-linked porcine acellular dermis. Non-cross-linked acellular porcine dermal matrix has been shown to result in successful hernia repair in 80% of patients with contaminated or

infected hernias in a retrospective review. Janfaza *et al* retrospectively compared SurgiMend, a non-cross-linked bovine acellular dermal matrix, to Flex HD, a non-cross-linked human acellular dermal matrix. They found higher rates of surgical site infections and hernia recurrence with Flex HD. Clemens *et al* conducted a prospectively collected, retrospectively analyzed study in which they compared hernia repair with Strattice, a non-cross-linked porcine acellular dermal matrix, and with SurgiMend, in 120 patients with mean follow-up of 21.0 months. They found no difference in the rate of recurrent hernia or bulge, although the Strattice group had a higher rate of overall complications due to a relatively higher rate of medical complications (pneumonia, renal failure) in that group not directly related to the type of mesh used.

At the Ohio State University Wexner Medical Center, the two most commonly used biologic meshes for hernia repair in the practice of the senior author ([name]) are Strattice and XenMatrix. These are both non-cross-linked porcine acellular dermal matrices, manufactured by different companies using different technologies. There are some structural differences between the two. For example, according to internal reports by the companies, XenMatrix has larger pores that allows more tissue ingrowth. However, there are no published reports comparing the performance profile those two meshes in the clinical setting.

## II. Objectives

Our goals in this study are:

- a. PRIMARY OUTCOME
  - i. To compare the **hernia recurrence rate** between XenMatrix and Strattice at **30 days and 1 year postoperatively**
- b. SECONDARY OUTCOMES
  - i. To compare the **bulge rate** between XenMatrix and Strattice at **30 days and 1 year postoperatively**
  - ii. To compare the **rate of Surgical Site Occurrences (SSOs)** between two non-cross-linked porcine dermal matrices (XenMatrix and Strattice) in abdominal wall reconstruction at **30 days and 1 year postoperatively**
    1. Infection
    2. Seroma
    3. Hematoma
    4. Wound dehiscence
    5. Skin necrosis
    6. Formation of enterocutaneous fistula
    7. Mesh infection
  - iii. To compare to changes in patient pain, physical functioning and quality of life after hernia repair between XenMatrix and Strattice, **preoperatively, and at 1 year postoperatively**
    1. **Pain** assessment: PROMIS Pain Intensity survey, PROMIS Pain Interference survey

2. **Physical functioning** assessment: PROMIS Physical Function
3. **Quality of life** assessment: HerQLes survey

### III. Procedures

#### a. Research design

This is a **prospective, randomized-controlled trial**. It is **single-blind** (patients are blinded to the type of mesh used while surgeons are not).

#### b. Sample

##### Inclusion criteria:

- Age > 18
- Patients presenting for elective hernia repair, with VHWG grade 2 or above
- Patients deemed to be good surgical candidates, with **no active life-threatening** cardiac disease, pulmonary disease, renal disease, hematologic disease
- Patients presenting for resection of large abdominal wall tumors who are expected to undergo have tumor extirpative defect that would require biologic mesh for closure

##### Exclusion criteria:

- Known allergy to porcine products
- Active smokers (within the past 4 weeks) presenting for elective hernia repair
- Patients with active life-threatening cardiac disease, pulmonary disease, renal disease, hematologic disease presenting for elective hernia repair
- Patients presenting for emergent hernia repair (in the setting of bowel strangulation, necrosis, penetrating trauma) as it will be difficult to consent those patients for the study preoperatively
- Patients with severe systemic sepsis
- Patients with frank purulence in the wound

##### Sample size (power analysis)

Our primary outcome is hernia recurrence rate at 30 days and 1 year postoperatively.

According to two industry-sponsored studies, the rate of hernia recurrence with XenMatrix is approximately 7%.

According to the large series by Clemens *et al*, the rate of hernia recurrence with Strattec is approximately 2.9%.

Assuming an alpha error of 5%, a power of 80%, and assuming a large standard deviation (3), the number of patients in each group that is needed to demonstrate a significant difference is 5.

In order to adequately power the study to analyze the secondary outcomes, **we plan to enroll 35 patients in each group (70 patients total)**

*a. Detailed study procedures*

When a patient with a ventral hernia or an abdominal wall tumor presents to the senior author for evaluation for abdominal wall reconstruction, a full history and physical examination will be performed. Patient who satisfy the study inclusion and exclusion criteria will be offered the opportunity to participate in the study. If they agree to participate, informed consent and HIPAA forms will be filled out and signed.

Patients will then be randomized to group A (Strattice) or group B (XenMatrix) using a random number generator made in Microsoft Excel. They will not be told which group they are in, and only the principal investigator, co-investigators and operating room staff will be aware of which mesh is being used.

The patients will be asked to fill out 4 surveys preoperatively: PROMIS Pain Intensity survey, PROMIS Pain Interference survey, PROMIS physical function survey and HerQLes survey.

They will then undergo surgery, and will be followed weekly for a month, then every 3 months for a year, and as needed. They will be evaluated for hernia recurrence, bulge, or other SSOs throughout the follow-up period.

They will be asked to fill out the PROMIS Pain Intensity survey, PROMIS Pain Interference survey, PROMIS physical function survey and HerQLes survey at 1 year.

*c. Measurements*

*The patient characteristics that will be collected will include:*

- 1) Age
- 2) Comorbidities
  - a. Diabetes
    - i. Hemoglobin A1c
  - b. Current tobacco use (defined as <4 weeks prior to surgery)
  - c. Former tobacco use (defined as >4 weeks prior to surgery)
  - d. Chronic Obstructive Pulmonary Disease
  - e. Coronary Artery Disease
  - f. Malnutrition (defined as prealbumin < 18 or albumin < 3.5)
  - g. Corticosteroid use
  - h. Use of other immunosuppressants
  - i. BMI
  - j. History of chemotherapy
  - k. History of radiation to abdomen
- 3) Hernia characteristics
  - a. Size on abdominal CT scan in cm^2
  - b. Ventral Hernia Working Group (VHWG) grade

- i. Grade 1 (low risk): no comorbidities, no history of wound infection, no contamination
- ii. Grade 2 (comorbid): smoker/obese/diabetic/immunosuppressed/COPD
- iii. Grade 3 (potentially contaminated): previous wound infection, stoma present, GI tract violated
- iv. Grade 4 (infected): infected mesh, septic dehiscence
- c. Number of prior hernia repairs

*The surgical details that will be collected will include*

- 1) Surgeon
- 2) Date of surgery
- 3) Wound class
  - a. Class I = clean
  - b. Class II = clean-contaminated
  - c. Class III = contaminated
  - d. Class IV = dirty
- 4) Whether bowel resection performed
- 5) Whether component separation technique (CST) performed
  - a. If yes, standard CST versus minimally-invasive CST
- 6) Whether fascia able to be primarily closed
- 7) Type of mesh used
- 8) Location of mesh
  - a. Overlay (superficial to the primary fascial repair)
  - b. Underlay (deep to the primary fascial repair)
    - i. Sub-rectus
    - ii. Intraperitoneal

*The outcome data that will be collected will include*

- a. Hernia recurrence
- b. Bulge
- c. SSOs
  - a. Infection
  - b. Seroma
  - c. Hematoma
  - d. Wound dehiscence
  - e. Skin necrosis
  - f. Formation of enterocutaneous fistula
  - g. Mesh infection
- d. Score on PROMIS Pain Intensity survey
- e. Score on PROMIS Pain Interference survey
- f. Score on PROMIS Physical Function
- g. Score on HerQLes survey

*d. Internal validity*

Since this is a randomized-controlled trial, we expect the baseline demographics and patient characteristics to be similar between the two groups, and we expect our results to be internally valid.

*e. External validity*

The study results will reflect the outcomes within our study population at the Ohio State University Medical Center, and may not be generalizable to other institutions.

*f. Data analysis*

Baseline patient characteristics will be compared between the two groups to ensure that the two groups are similar and that there are no confounders

Multiple binary logistic regression will be performed to detect predictors of hernia recurrence, bulge and other SSOs. It will also be used to determine whether one mesh has a higher rate of complications compared to the other.

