CDC wound class	20			$\chi^2_3=3.64, P=0.30^2$
1		6/12 (50.00)	5/8 (62.50)	
2		3/12 (25.00)	2/8 (25.00)	
3		0/12 (0.00)	1/8 (12.50)	
4		3/12 (25.00)	0/8 (0.00)	
VHWG grade	20			$\chi^2_3=4.49, P=0.21^2$
1		0/12 (0.00)	1/8 (12.50)	
2		6/12 (50.00)	2/8 (25.00)	
3		4/12 (33.33)	5/8 (62.50)	
4		2/12 (16.67)	0/8 (0.00)	
Kanters grade	20			$\chi^2_1=0.83, P=0.36^2$
1		0/12 (0.00)	0/8 (0.00)	
2		5/12 (41.67)	5/8 (62.50)	
3		7/12 (58.33)	3/8 (37.50)	
Primary fascial repair : Yes	19	9/12 (75.00)	6/7 (85.71)	$\chi^2_1=0.31, P=0.58^2$
Unilateral component separation : Yes	20	1/12 (8.33)	0/8 (0.00)	$\chi^2_1=0.70, P=0.40^2$
Bilateral component separation : Yes	20	4/12 (33.33)	7/8 (87.50)	$\chi^2_1=5.69, P=0.02^2$
Bridged repair : Yes	19	4/12 (33.33)	1/7 (14.29)	$\chi^2_1=0.83, P=0.36^2$
Mesh position ^{cata}				
Onlay mesh placement : Yes	20	0/12 (0.00)	0/8 (0.00)	NA
Underlay mesh placement : Yes	20	12/12 (100.00)	6/8 (75.00)	$\chi^2_1=3.33, P=0.07^2$
Inlay mesh placement : Yes	20	1/12 (8.33)	1/8 (12.50)	$\chi^2_1=0.09, P=0.76^2$
Sublay mesh placement : Yes	20	0/12 (0.00)	2/8 (25.00)	$\chi^2_1=3.33, P=0.07^2$

Note:

N is the number of non-missing value. 1 Kruskal-Wallis. 2 Pearson. 3 Wilcoxon.

Stat, P is the test statistic and p-value.

cata = check all that apply

6-week Outcomes

Table 3a: 6-week outcomes, randomized patients

Variables	N	Strattice	XenMatrix	Test Statistic
		(N=16)	(N=30)	
Bulge : Yes	46	0/16 (0.00)	0/30 (0.00)	NA
Recurrence : Yes	46	0/16 (0.00)	0/30 (0.00)	NA
SSO within 6 weeks : Yes	46	1/16 (6.25)	11/30 (36.67)	$\chi^2_1=5.01, P=0.03^2$
SSO Type (cata)				
Skin necrosis : Yes	46	0/16 (0.00)	1/30 (3.33)	$\chi^2_1=0.55, P=0.46^2$
Enterocutaneous fistula : Yes	46	0/16 (0.00)	2/30 (6.67)	$\chi^2_1=1.12, P=0.29^2$
Dehiscence : Yes	46	0/16 (0.00)	1/30 (3.33)	$\chi^2_1=0.55, P=0.46^2$
Seroma : Yes	46	0/16 (0.00)	2/30 (6.67)	$\chi^2_1=1.12, P=0.29^2$
Hematoma : Yes	46	0/16 (0.00)	0/30 (0.00)	NA
Infection : Yes	46	1/16 (6.25)	10/30 (33.33)	$\chi^2_1=4.21, P=0.04^2$
Mesh infection : Yes	46	0/16 (0.00)	3/30 (10.00)	$\chi^2_1=1.71, P=0.19^2$

Note:

N is the number of non-missing value. 1 Kruskal-Wallis. 2 Pearson. 3 Wilcoxon.

Stat, P is the test statistic and p-value.

cata = check all that apply

Table 3b: 6-week outcomes, observational patients

Variables	N	Strattice	XenMatrix	Test Statistic
		(N=12)	(N=8)	
Bulge : Yes	20	0/12 (0.00)	0/8 (0.00)	NA
Recurrence : Yes	20	1/12 (8.33)	0/8 (0.00)	$\chi^2_1=0.70, P=0.40^2$

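### Recurrence at 30 days and at 1 year are joint primary outcomes with no rule for which decides; the 30-day comparison can hardly inform, and the SAP reports no 1-year result

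*Protocol*

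**What the plan says.** The Protocol's section II (Objectives) gives the primary aim as "To compare the hernia recurrence rate between XenMatrix and Strattice at 30 days and 1 year postoperatively". The sample-size paragraph in section III repeats it: "Our primary outcome is hernia recurrence rate at 30 days and 1 year postoperatively". That paragraph then sets one alpha (5%), one power (80%) and two planning rates, 7% for XenMatrix and 2.9% for Strattice. It derives 5 patients per group and raises this to 35 per group for the secondary outcomes. It ties neither the alpha nor the rates to a time point.

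The Background describes the series behind the 2.9% as having "mean follow-up of 21.0 months". Neither document gives a follow-up time for the 7%.

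The Data analysis section plans multiple binary logistic regression for recurrence. It gives no time point, order of testing, alpha split, or statement of whether either or both comparisons must succeed.

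The SAP takes surgical site occurrence within 6 weeks as its primary analysis and says other outcomes had too few events to analyse. Recurrence appears only in the 6-week outcome tables (3a and 3b).

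**The concern.** A reader cannot tell what result would answer the primary question. A difference at 30 days only, at 1 year only, or at both could each be called the primary finding. So could a null result at 30 days, which would be expected whether or not the meshes differ, because few recurrences can be seen that early.

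The one time point that could carry information, 1 year, has no protected status. The SAP's only recurrence result for randomized patients is an early one with no events. Had 1 year been ranked first, the absence of a 1-year result would stand out as a missing primary analysis.

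**Working it through.** **Inputs.** 7% and 2.9%, alpha 5%, power 80%, SD 3, 5 and 35 per group (Protocol, sample-size paragraph); last follow-up by arm (SAP Table 1a); recurrences by 6 weeks (SAP Tables 3a and 3b). Sidedness is not stated, so two-sided is assumed.

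**The plan's own figure.** Five per group can be reproduced only with a one-sample formula for a mean, using a difference of 4.1 percentage points and SD 3: (3 × (1.960 + 0.842) / 4.1)² = 4.2, rounded up to 5. The two-group version doubles this to 8.4, so 9 per group. Neither suits a binary outcome, and neither refers to a time point.

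**Power at 30 days, 35 per group.** Let f be the share of the 7% and 2.9% recurrences that occur by day 30. This is an assumption, because the documents give no 30-day rate. Expected events are 35 × 0.07 × f and 35 × 0.029 × f. The chance of no event in either arm is [(1 − 0.07f)(1 − 0.029f)]^35. Power comes from exact binomial enumeration of the chi-square test.

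| f | Expected events, XenMatrix / Strattice | Chance of no event | Chi-square power |
|---|---|---|---|
| 10% | 0.25 / 0.10 | 71% | 0.01% |
| 25% | 0.61 / 0.25 | 42% | 0.25% |
| 50% | 1.2 / 0.5 | 17% | 2.1% |
| 100% | 2.45 / 1.02 | 3% | 9.5% |

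Fisher's test gives 1.3% at f = 100%. With no events in one arm, significance needs at least 4 in the other by chi-square (p = 0.039) or 6 by Fisher (p = 0.025). If both time points had to succeed, power could not exceed the 30-day figure.

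**Type I error if either time point may win.** For two independent tests, 1 − 0.95² = 9.75%. Here the outcomes are nested, since a recurrence by day 30 is also one by 1 year, and events are few. Simulation at 35 per group, with a common 1-year rate of about 5% to 7% and f from 10% to 50%, gives about 3.6% to 6.3% by chi-square and no more than about 0.7% by Fisher.

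**Early recurrences observed by 6 weeks.**
- Randomized: 0/16 Strattice, 0/30 XenMatrix, test not computable.
- Observational: 1/12 Strattice, 0/8 XenMatrix.
- Together: 1/66.

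Randomized XenMatrix follow-up starts at 0 days, so not every patient counted as event-free was necessarily seen to day 30.

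**Power at 1 year, if 7% and 2.9% are taken as 1-year rates.** The mean rate is 0.0495. The two-proportion formula gives n = [1.960 × √(2 × 0.0495 × 0.9505) + 0.842 × √(0.07 × 0.93 + 0.029 × 0.971)]² / 0.041² ≈ 439 per group. At 35 per group the same approximation gives 12.0% power.

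**Follow-up by randomized arm (Table 1a).** The lower quartile of last follow-up is 140.92 days for XenMatrix and 727.67 days for Strattice; the medians are 544.00 and 1157.50 (P = 0.02). About a quarter of the XenMatrix arm was last seen before 5 months. A crude 1-year proportion, or a binary regression on it, would count those patients as recurrence-free without having observed them.

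**The case against.** The best case against the point is that it changes little. The SAP never presents a 30-day null as a primary result, and it openly marks the recurrence test as not computable. Its move to surgical site occurrences is a separate and more visible problem. The 5-per-group calculation is a larger error in the same paragraph, and naming 1 year does not rescue a trial with about 12% power. All of this stands. It limits the weight of the point but does not supply the missing rule or the missing 1-year result.

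Some stronger readings should be resisted:

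- A reader might infer a family-wise error of 9.75%. That needs independent, informative tests; these are nested and sparse.
- A reader might call a 30-day null guaranteed. The zero counts are hindsight from 46 patients rather than the planned 70. At the planning stage, low power depends on the assumed f, although it is low over the whole range.
- A reader might say that neither planning rate is a 30-day rate. The documents support this only for the 2.9%.
- A reader might say that there were no early recurrences. Table 3b shows one.
- A reader might say that the alpha belongs to no test at all. Logistic regression is named; the time point and the success rule are what is missing.

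The 1-year estimate is not clean either. Kaplan-Meier removes bias from unequal follow-up only if censoring is unrelated to recurrence, and designating the primary time point after enrolment has ended is post hoc.

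**Conclusion.** The point holds. The protocol has two unranked primary time points, one alpha, one sample size and no deciding rule, and the SAP does not fill the gap. The 30-day comparison has at most about 2% power if up to half of the recurrences occur by then, and 9.5% if all do. This rests on the protocol's own rates, 35 per group and a two-sided chi-square test.

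The consequence is that success is undefined and the informative time point is unreported; the false-positive rate is not materially affected. The 12% and 439 figures further assume that 7% and 2.9% are 1-year rates, which the documents do not say. The point merits correction, but it does not by itself overturn any result in the SAP.

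**What to change.** - In the Objectives and the sample-size paragraph, name hernia recurrence by 1 year as the single primary outcome, attach the 5% alpha to it, and make 30-day recurrence descriptive.
- Add to the SAP, labelled as a post hoc clarification, 1-year recurrence by randomized arm from Kaplan-Meier, with confidence intervals for each arm and for the difference. If an arm has no events, use an exact-type interval, because the usual variance formula then gives zero width.
- State the non-informative censoring assumption and add a simple sensitivity analysis, for example varying the recurrence rate assumed for patients last seen before 1 year.
- Restate the power: about 12% at 35 per group against about 439 per group for 80%, if the planning rates are read as 1-year rates. Present the 1-year result as an estimate.

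The cost is a few sentences and one table. The protocol schedules recurrence checks every 3 months to 1 year, so the data should largely exist, but some XenMatrix patients lack 1-year follow-up. The price is a wide interval and a much less favourable statement of power.

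### The sample-size paragraph plans a 30-day and 1-year recurrence endpoint on one undated rate per mesh, and neither rate is shown to apply at either time

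*Protocol*

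**What the plan says.** The primary objective (Protocol, II. Objectives) is to compare recurrence "between XenMatrix and Strattice at 30 days and 1 year postoperatively". The sample-size paragraph repeats it: "Our primary outcome is hernia recurrence rate at 30 days and 1 year postoperatively". Under the detailed study procedures, patients "will be followed weekly for a month, then every 3 months for a year, and as needed", so scheduled observation ends at one year.

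The same paragraph gives the planning rates. For XenMatrix, citing references 17 and 18, "the rate of hernia recurrence with XenMatrix is approximately 7"%. For Strattice, citing reference 15, "the rate of hernia recurrence with Strattec is approximately 2.9"%. No time point is attached to either. With an alpha of 5%, power of 80% and a standard deviation of 3, it concludes that "the number of patients in each group that is needed to demonstrate a significant difference is 5". It then sets enrolment at 35 per group, which it says is for the secondary outcomes.

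The follow-up of reference 15 appears only in the Background and rationale, which describes a comparison of Strattice with a bovine matrix "in 120 patients with mean follow-up of 21.0 months". The follow-up of references 17 and 18 is not given in either document.

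**The concern.** Recurrence accumulates with time, and the Background itself quotes recurrence risks over five years. A planning rate therefore needs a time point, and it should be the time point of the endpoint. Here a single undated rate per mesh is set against two time points. One rate could serve both only if every recurrence fell within 30 days, which the protocol does not claim.

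The one follow-up figure that is available, 21.0 months, is longer than either endpoint time. The XenMatrix window is unknown. Some of the 7% versus 2.9% contrast could therefore reflect length of follow-up rather than mesh.

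At stake are the expected number of primary events, the assumed difference and any power statement. Correcting the sample-size formula while keeping these rates would still size an outcome not shown to be the one defined.

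**Working it through.** **Inputs.** Rates 7% and 2.9%, alpha 5%, power 80%, SD 3 and 35 per group are from the sample-size paragraph. Mean follow-up of 21.0 months is from the Background. Two-sided testing is assumed, because sidedness is not stated. z = 1.960 and 0.8416.

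**1. The plan's own figure.** The difference is 7 − 2.9 = 4.1 points. Treating percentages as means with SD 3:
- Two-group formula: 2 × (3 × (1.960 + 0.8416) / 4.1)² = 8.40, so 9 per group.
- Without the factor 2 for two groups: 4.20, so 5.

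The stated 5 thus matches a one-sample formula for a continuous outcome. With 5 per group, even the two-means calculation has only 58% power. This error is separate from the time window.

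**2. Rates at face value, as proportions.** n = [1.960 √(2p̄(1−p̄)) + 0.8416 √(p₁(1−p₁) + p₂(1−p₂))]² / (p₁−p₂)², with p̄ = 0.0495:
- [1.960 × 0.3068 + 0.8416 × 0.3054]² / 0.041² = 438.2, so 439 per group.
- Power at 35 per group, by exact enumeration of the uncorrected chi-square test, is 9.5%. The normal approximation gives about 12% and Fisher's exact test about 1%.
- Expected recurrences: 35 × (0.07 + 0.029) = 3.5.

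**3. Sensitivity to the window.** The documents give no 1-year rate, so this step rests on assumptions. Suppose a constant hazard and treat 2.9% as a cumulative 21-month risk. Then the 1-year rate is 1 − (1 − p)^(12/21): 2.9% becomes 1.67%, and 7%, if it too were a 21-month rate, becomes 4.06%.

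| Assumption | 1-year rates, XenMatrix v Strattice | n per group | Power at 35 per group (exact chi-square) | Expected events in 70 |
|---|---|---|---|---|
| Both rates already hold at 1 year | 7% v 2.9% | 439 | 9.5% | 3.5 |
| Both are 21-month rates | 4.06% v 1.67% | 761 | 3.1% | 2.0 |
| Only Strattice rescaled | 7% v 1.67% | 228 | 13.8% | 3.0 |

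**4. How far the illustrations depend on the assumptions.**
- *XenMatrix follow-up.* With Strattice at 1.67%, an assumed 9 months puts the 1-year XenMatrix rate at 9.2% (141 per group). An assumed 24 months puts it at 3.6% (1,112 per group).
- *Shape of the hazard.* If the hazard rises with time (Weibull shape 1.5 or 2, assumed), the 1-year Strattice rate is 1 − 0.971^((12/21)^shape) = 1.3% or 1.0%. Constant hazard is therefore not a floor.

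**5. Thirty days.** Under the same constant hazard, with both treated as 21-month rates and 30 days taken as one month, the rates are about 0.34% and 0.14%. That is 35 × (0.0034 + 0.0014) = 0.17 expected recurrences in 70 patients.

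**The case against.** The strongest reply has three parts.

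*The mismatch is only partly documented.* The 21.0 months is a mean over 120 patients and both meshes in the source series. No follow-up for the Strattice arm and no timing of events is given, and a crude proportion under variable follow-up is not a 21-month cumulative risk. All the Strattice recurrences may have occurred in the first year, and the 7% may already be a 1-year rate. This stands. A reader might infer that 2.9% and 7% are wrong for one year, that they are not 30-day rates, or that 1.7% is the true 1-year Strattice figure. The documents support none of these. They support only that neither rate is shown to apply at the endpoint times.

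*The formula error is much larger.* Moving from 5 to 439 per group owes nothing to the window, and power at 35 per group is very low in every row of the table. This also stands, and it is why the two corrections belong together. It does not make the time point dispensable, because a recalculation that keeps undated rates inherits the gap.

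*The practical effect is limited.* Enrolment of 35 per group was justified by the secondary outcomes. According to the SAP, the randomized trial stopped early (its tables show 46 randomized patients), the analysis is of surgical site occurrences within six weeks, and other outcomes had too few events to analyse. Dating the planning rates changes no reported result. This stands as a limit on the consequence: what is affected is the protocol's statement of what the design could detect.

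**Conclusion.** The point holds in a limited form. The primary outcome is set at 30 days and 1 year, but the planning rates are undated. One comes from a series averaging 21.0 months of follow-up, and the other from studies whose follow-up is not stated. Neither rate, nor the 4.1-point difference, is shown to be that of the endpoint.

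A reader might infer that the trial must be weaker than the rates imply. The direction is in fact unknown: relative to 439 per group at face value, the illustrations go up to 761 and down to 228. Those two figures depend on constant hazard and on the XenMatrix follow-up chosen, so they are examples and not limits.

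What does not depend on the scenario is that the stated 5 per group at 80% power is not delivered under any of these rates. In the three table scenarios, power at 35 per group is about 3% to 14%. Most of that shortfall comes from treating percentages as means, not from the time window.

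**What to change.** In the Protocol's sample-size paragraph:

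- State the follow-up behind each planning rate, including that of references 17 and 18.
- Name 1 year as the time point being sized, and give a sourced or explicitly assumed 1-year recurrence rate for each mesh. Do not enter 1.7% as a lower limit for Strattice.
- Say that neither rate is shown to be a 30-day rate.
- Replace the 5 per group with a two-proportion calculation that states its sidedness and reports the required number and the power at 35 per group over a range of 1-year rates. The face-value case (about 439 per group, about 10% power) should be one entry, with any rescaled cases labelled as illustrations.

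Make this change together with the correction of the sample-size formula. The cost is some protocol wording and a short recalculation, with no change in enrolment. The drawback is that the stated power becomes a range and looks less favourable.
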